##### TYPE OF PARTICIPANT

2. Participants who are otherwise healthy (other than the acceptable condition of asthma and other mild atopic diseases, including allergic rhinitis and atopic dermatitis) as determined by medical evaluation based on screening medical history, physical examination, vital signs, ECG assessment, pulmonary function testing, laboratory tests and cardiac monitoring.
  - **Note:** A participant with a clinical abnormality or laboratory parameter(s) not specifically listed in the exclusion or exclusion criteria that is outside the reference range for the population being studied may be included only if the investigator, in consultation with the Medical Monitor (if required), agree and document that the finding is unlikely to introduce additional risk factors and will not interfere with the study procedures.
3. A current confirmed physician diagnosis of asthma (as defined by the British Thoracic Society/ Scottish Intercollegiate Guidelines Network ([BTS/SIGN](#), 2019), or the Global Initiative for Asthma ([GINA](#), 2020 guidelines)) at least 6 months before screening. The reason for diagnosis of asthma should be documented in the participant's source data, including relevant history.

4. A screening pre-bronchodilator FEV1  $\geq$  65% predicted normal value.  
**Note:** Predicted values based on European Respiratory Society (ERS) guidelines [Quanjer, 2012].

5. Participants with maintained control of their asthma using the permitted medications listed below, will be recruited as follows:

Permitted Medication Use	Number of Participants
SABA use and/or intermittent ICS/LABA use.	n=8
Regular treatment with ICS or ICS/LABA (including use of Leukotriene Receptor Agonist (LTRA))	n=8

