### 7.2.5. Spirometry Stopping Criteria

Any participant experiencing a reduction in FEV1 at the 1-hour post-dose time point compared to daily predose value of > 25% in Parts A and B and > 20% in Part C will be withdrawn from the study.

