#### 8.1.5. Clinical Safety Laboratory Assessments

- See [Appendix 2](#) for the list of clinical laboratory tests to be performed and to the SoA for the timing and frequency.
- The Investigator must review the laboratory report, document this review, and record any clinically significant changes occurring during the study as an AE. The laboratory reports must be filed with the source documents.

- In Part C, abnormal laboratory findings associated with the underlying disease are not considered clinically significant, unless judged by the Investigator to be more severe than expected for the participant's condition.
- All laboratory tests with values considered clinically significantly abnormal during participation in the study should be repeated until the values return to normal or baseline or are no longer considered significantly abnormal by the Investigator or Medical Monitor.
  - If clinically significant values do not return to normal/baseline within a period of time judged reasonable by the Investigator, the aetiology should be identified, and the Sponsor notified.
- All protocol-required laboratory tests, as defined in Section 10.2, must be conducted in accordance with the SRM and the SoA (Section 1.3).
- If laboratory values from non-protocol specified laboratory tests performed at the institution's local laboratory require a change in participant management or are considered clinically significant by the Investigator (e.g., SAE or AE or dose modification), then the results may be recorded in the eCRF.

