4.2.1. Definition of endpoints

Adverse events will be coded using the standard Medical Dictionary for Regulatory Affairs (MedDRA dictionary).

Grade 1 AEs are defined as mild. Grade 2 or higher AEs are defined as moderate or severe. This study will report AEs as mild, moderate or severe.

A study intervention-related AE/SAE is defined as an AE/SAE for which the investigator classifies the possible relationship to study intervention as "Yes". A worst-case scenario approach will be taken to handle missing relatedness data, i.e. the summary table will include events with the relationship to study intervention as 'Yes' or missing.

Spirometry assessments are performed in triplicate with the highest value reported.

Clinically significant values are defined as:

- Values in the potential clinical interest (PCI) ranges for laboratory values, vital signs and ECGs
- Values that achieve the study stopping criteria (protocol section 7.2.5) for spirometry

The same PCI ranges will be used for both healthy volunteers and stable asthmatics, with all ranges being defined in the OPS.

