4.2.2.2. Laboratory Data, Vital Signs, ECGs and Spirometry

For laboratory data, separate tables for haematology, clinical chemistry and urinalysis tests will be produced. Liver biochemical parameters will be included with clinical chemistry tests. Vital signs data will include semi supine systolic and diastolic blood pressure, pulse rate, respiratory rate and temperature measurements.

ECG data will include PR, QRS, QT and QTcF intervals.

Spirometry data will include FEV₁ and FVC measurements.

For haematology, clinical chemistry, urinalysis, vital signs, ECG and spirometry data the following information will be summarised:

1. Clinically significant values at each visit
2. Raw and change from baseline values at each visit

Note: The first table is the only one included as part of the primary endpoint. [redacted]

[redacted]

In order to detect potential bronchospasms, an additional table for spirometry values will be produced which summarises the changes between daily pre- and post-dose FEV₁ and FVC values.

For ECGs, a figure plotting the baseline QTcF and the worst-case post-baseline values will be produced. The figure will have reference lines at 480 and 500 msec for both the ordinate and the abscissa axes. There will be diagonal reference lines at equality (i.e. a 45 degree line), at equality plus 30 msec, and at equality plus 60 msec.

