4.7. Changes to the Protocol Defined Statistical Analysis Plan

There were no changes or deviations to the originally planned statistical analysis specified in the protocol (Dated: 24-Sep-2021).

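### The SAP's clinical-significance rule has no visible baseline condition, so laboratory, vital-sign or ECG values abnormal before dosing can count in the primary table; for Part C laboratory values it also conflicts with Protocol 8.1.5

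*SAP*

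**What the plan says.** SAP 4.2.1 gives two definitions of a clinically significant value. For laboratory values, vital signs and ECGs it is: "Values in the potential clinical interest (PCI) ranges for laboratory values, vital signs and ECGs". For spirometry it is: "Values that achieve the study stopping criteria (protocol section 7.2.5) for spirometry". On the ranges it says: "The same PCI ranges will be used for both healthy volunteers and stable asthmatics, with all ranges being defined in the OPS".

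SAP 4.2.2.2 plans two summaries for each data type. The first is "Clinically significant values at each visit" and the second is raw values and change from baseline. Only the first belongs to the primary endpoint. Redacted text follows that note.

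Protocol 8.1.5 says: "In Part C, abnormal laboratory findings associated with the underlying disease are not considered clinically significant", with an exception where the investigator judges the finding more severe than expected for the participant's condition. Protocol 9.4.1.2 limits the primary endpoint to clinically significant measurements between randomisation and follow-up, and leaves the PCI ranges to the SAP. SAP 4.7 states: "There were no changes or deviations to the originally planned statistical analysis specified in the protocol".

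SAP 4.1.2 already defines baseline as the latest non-missing pre-dose value, taken separately for each treatment period in Part A.

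**The concern.** A primary safety table should help the reader separate what happened after dosing from what was there before. Under the visible rule, a participant whose value was in a PCI range before the first dose, and stays there, can be counted at each later visit with no change at all.

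This matters most in Part C. Its participants are otherwise healthy "other than the acceptable condition of asthma and other mild atopic diseases, including allergic rhinitis and atopic dermatitis", may be up to 65 years old (50 in Parts A and B), and may enter with an out-of-range laboratory parameter if it is documented as unlikely to add risk. Eosinophils are in the haematology panel and are one plausible candidate. With 12 participants on active and 4 on placebo, a few stable abnormalities could look like a drug signal, or raise the background enough to blur a real one.

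The two primary components could also treat one finding differently. Protocol 10.3.1 keeps disease-associated findings out of the AE definition unless they are more severe than expected, while the PCI rule can count the same value as clinically significant.

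**Working it through.** **1. The definitions side by side, for a Part C laboratory value associated with asthma or atopy and no worse than expected**

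| Source | Clinically significant? |
|---|---|
| Protocol 8.1.5 | No |
| Protocol 9.4.1.2 | Refers to PCI ranges; no exception for the underlying disease |
| SAP 4.2.1 | Yes, if the value is in a PCI range |
| SAP 4.7 | Declares no change from the protocol |

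The first and third rows disagree whenever such a value lies in a PCI range. The second row shows that the tension already exists inside the protocol.

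**2. Which data types are affected**

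- Laboratory values: missing baseline condition in all parts, plus the conflict with 8.1.5 in Part C.
- Vital signs and ECGs: missing baseline condition only. Protocol 8.1.5 does not mention them.
- Spirometry: not affected. Protocol 7.2.5 judges FEV1 against the "daily predose value of > 25% in Parts A and B and > 20% in Part C", so a low FEV1 present before dosing does not count by itself.

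**3. The plan's own figures**

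For 12 active participants, Protocol 9.2 and SAP 5 give the chance of no event as 54% at a 5% rate and 7% at a 20% rate. The formula is (1 − p)^12:

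- 0.95^12 = 0.540
- 0.80^12 = 0.069

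Both reproduce.

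**4. How often a stable background would appear on active only**

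Inputs: 12 active and 4 placebo participants (SAP 1.2). Let p be the proportion of Part C participants with a persistent pre-dose PCI value for a given parameter. The documents give no value for p, so 5% to 30% is an assumption, with 2% added to show a lower case. Participants are taken as independent, with the same p in both arms and both strata, and no drug effect.

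P(at least one on active and none on placebo) = (1 − p)^4 × [1 − (1 − p)^12]

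| p | (1 − p)^4 | 1 − (1 − p)^12 | Active only | Expected active (12p) | Expected placebo (4p) |
|---|---|---|---|---|---|
| 2% | 0.922 | 0.215 | 20% | 0.24 | 0.08 |
| 5% | 0.815 | 0.460 | 37% | 0.6 | 0.2 |
| 10% | 0.656 | 0.718 | 47% | 1.2 | 0.4 |
| 20% | 0.410 | 0.931 | 38% | 2.4 | 0.8 |
| 30% | 0.240 | 0.986 | 24% | 3.6 | 1.2 |

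If values already in range at baseline were not treated as new events, the contribution from this source would be zero in every row.

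**5. Why any movement further out should not count as new**

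Part C has one baseline laboratory sample (Day -1) and four later ones (Days 2, 4, 6 and 8). For a stable abnormal value, treat the five readings as exchangeable without ties. The baseline is then the most extreme with probability 1/5, so at least one later reading lies further out with probability 4/5. A rule that counted any outward movement would bring back about 80% of the stable cases.

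**The case against.** The strongest reply is that SAP 4.2.1 does what Protocol 9.4.1.2 asks. Section 8.1.5 concerns how the investigator reviews laboratory reports, records AEs and repeats tests; 9.4.1.2 is the endpoint rule and it uses PCI ranges. On that view SAP 4.7 is defensible. This stands in part: the tension lies within the protocol as well as between the documents. But both sections use the term clinically significant, and nothing says which meaning applies to Part C laboratory values.

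Second, the cut-offs are unseen. Nothing shows that eosinophils have a PCI range or that mild atopy would reach it, and a baseline restriction in the redacted text cannot be ruled out. This stands: such values can count, but are not shown to count. Entry criteria also remove some candidates (raised ALT and AST, raised bilirubin with an exception, QTcF above 450 msec). Part C inclusion criterion 2 requires participants to be otherwise healthy on ECG, vital signs and laboratory tests.

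Third, the 24% to 47% largely reflects the 12:4 allocation, and any background event would behave alike. That is true. The difference here is that the baseline is measured, so the pre-existing part can be separated.

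Fourth, change-from-baseline tables, a plot of baseline against worst post-baseline QTcF, a placebo group and the absence of hypothesis tests limit the harm. They do, but the tables that would show a stable abnormality are outside the primary endpoint.

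Using one set of ranges for both populations is a legitimate choice that helps comparison across parts, and it need not change.

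**Conclusion.** The point holds for laboratory, vital-sign and ECG values: the visible rule has no baseline condition, so abnormalities present before dosing can enter the primary by-visit table. For Part C laboratory values there is also an unresolved conflict with Protocol 8.1.5, shared with Protocol 9.4.1.2.

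The size is unknown. The 24% to 47% holds only for an assumed persistent prevalence of 5% to 30% for a given parameter; at 2% it is 20%. It is not a forecast for any planned table.

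A reader might infer more than the documents support:

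- **That 8.1.5 also covers ECGs and vital signs.** It names laboratory findings only. Part C lacks the numeric heart-rate, PR and QRS exclusions of Parts A and B, but this does not make such values disease-related.
- **That pre-dose values are themselves primary events.** The protocol window opens at randomisation on Day 1, so the Day -1 laboratory sample falls outside it. An existing laboratory abnormality would count by persisting at later visits.
- **That spirometry shares the problem.** It does not.
- **That a baseline flag puts 8.1.5 into effect.** It does not: 8.1.5 rests on investigator judgement, and a new disease-associated value would still be flagged.

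The analyses are descriptive, so this is an inexpensive improvement to a primary safety table and not a threat to the study's conclusions.

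**What to change.** In SAP 4.2.1 and 4.2.2.2:

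1. Restrict the primary laboratory, vital-sign and ECG count to post-dose values, meaning after the first dose, or after that period's dose in Part A. The wording matters because Part C laboratory samples on Days 2, 4 and 6 are drawn before that day's dose and must stay in.
2. Split the count by whether the participant's baseline (SAP 4.1.2; per period in Part A) was already in the PCI range in the same direction. Treat only values not in range at baseline as new events.
3. Keep the total count, and show values already in range at baseline in a separate column.
4. Read worsening from the planned change-from-baseline table, not from any outward movement.
5. Leave spirometry unchanged.

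Separately, state which definition of clinical significance governs Part C laboratory values, reconciling Protocol 8.1.5, Protocol 9.4.1.2 and SAP 4.2.1, and list any departure in SAP 4.7.

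The cost is SAP and OPS wording, one programming flag on data already collected, and a slightly longer table. Because the total is kept, no information is lost.

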4.2.2. Main analytical approach

4.2.2.1. Adverse events and serious adverse events

Adverse events analyses including the analysis of adverse events (AEs) and Serious AEs (SAEs) will be based on GSK Core Data Standards. All summaries will be tabulated by study intervention, cohort and dose, except for Cohorts 3 and 4. As cohorts 3 and 4 are identical in every aspect except the timing of bronchoscopy assessment, data from the two cohorts will be pooled and reported together.

An overview summary of AEs, including counts and percentages of participants with any AE, AEs related to study intervention, moderate and severe AEs, moderate and severe AEs related to study intervention, AEs leading to permanent discontinuation of study intervention, study intervention related AEs leading to permanent discontinuation of study intervention, AE leading to dose reductions, AEs leading to dose delays, SAEs, SAEs related to study intervention, fatal SAEs, and fatal SAEs related to study intervention as well as bronchoscopy related AEs will be produced.

The frequency and percentage of AEs will be summarized and displayed in two ways: 1) in descending order by preferred term (PT) only and 2) in descending order by system organ class (SOC) and PT.

All SAEs will be tabulated based on the number and percentage of participants who experienced the event.

Separate summaries will also be provided for study intervention-related AEs and SAEs, AEs leading to permanent discontinuation of study intervention and study intervention related AEs leading to permanent discontinuation of study intervention. These summary tables will be displayed by PT.

4.2.2.2. Laboratory Data, Vital Signs, ECGs and Spirometry

For laboratory data, separate tables for haematology, clinical chemistry and urinalysis tests will be produced. Liver biochemical parameters will be included with clinical chemistry tests. Vital signs data will include semi supine systolic and diastolic blood pressure, pulse rate, respiratory rate and temperature measurements.

ECG data will include PR, QRS, QT and QTcF intervals.

Spirometry data will include FEV₁ and FVC measurements.

For haematology, clinical chemistry, urinalysis, vital signs, ECG and spirometry data the following information will be summarised:

1. Clinically significant values at each visit
2. Raw and change from baseline values at each visit

Note: The first table is the only one included as part of the primary endpoint. [redacted]

[redacted]

In order to detect potential bronchospasms, an additional table for spirometry values will be produced which summarises the changes between daily pre- and post-dose FEV₁ and FVC values.

For ECGs, a figure plotting the baseline QTcF and the worst-case post-baseline values will be produced. The figure will have reference lines at 480 and 500 msec for both the ordinate and the abscissa axes. There will be diagonal reference lines at equality (i.e. a 45 degree line), at equality plus 30 msec, and at equality plus 60 msec.

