**Footnotes to Part C: Repeat Dose | Asthma (Cohort 5)**

1. Day -1 inhaler training may be performed on Day 1 if needed and before administration of the first dose. Additional training may be provided as needed and according to Investigator discretion.
2. To be performed according to local site procedures. Additional ad hoc testing may be implemented based on local site procedures.
3. Predose and 30 min only.
4. PEF measurements will be taken in triplicate twice each day (once in morning upon waking and once in the evening before bedtime) from Day -1 evening until discharge on Day 8. Clinical site staff will complete and record the PEF measurements at each time point.
5. Provide PEF device refresher training if necessary.
6. Includes systolic and diastolic blood pressure, heart rate, respiration rate and tympanic temperature.
7. Predose only
8. On treatment days ECGs will be collected at predose and 6-hours post-dose. On Day 1 predose, triplicate measurements will be collected, and the mean values will be used to calculate baseline. At all other times single ECGs can be taken.
9. Cardiac telemetry to start approximately 1-hour pre-dose and continuously until 6 hours post dose.
10. Clinical Chemistry and Haematology only.
11. At pre-dose, 5 min, 15 min, 30 min, 45 min, 1 h, 2 h, 4 h, 6 h, 8 h, 12 h and 16 h

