**9.4.1.2. Laboratory values, vital signs, 12-lead electrocardiogram and Spirometry**

Whilst all data collected will be summarized, only measurements which are clinically significant at any timepoint between randomisation and follow up will be reported as part of the primary endpoint. Potential clinical interest (PCI) ranges will be defined in the SAP.

This data includes:

- Laboratory results for haematology, clinical chemistry and urinalysis (see [Appendix 2](#) for full details).
- Vital Signs measurements for semi supine systolic and diastolic blood pressure, pulse rate, respiratory rate and temperature
- 12-lead safety electrocardiogram (ECG) measurements for heart rate, PR, QRS, QT and QT interval corrected for heart rate according to Frederica's formula (QTcF) intervals
- Spirometry measurements for FEV1 and FVC

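### The SAP's ECG list omits heart rate, which the protocol counts in the primary safety endpoint; in Part C this leaves same-day post-dose heart rate out of every ECG and vital-signs table.

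*SAP*

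**What the plan says.** Protocol 9.4.1.2 lists the data behind the second part of the primary endpoint. For ECG these are "12-lead safety electrocardiogram (ECG) measurements for heart rate, PR, QRS, QT and QT interval corrected for heart rate", the correction being Fridericia's. The section opens with a general commitment, "Whilst all data collected will be summarized", and then limits the endpoint itself: "only measurements which are clinically significant at any timepoint between randomisation and follow up will be reported as part of the primary endpoint".

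SAP 4.2.2.2 gives the matching list for analysis: "ECG data will include PR, QRS, QT and QTcF intervals". It plans two tables for each data type: clinically significant values by visit, and raw values with change from baseline by visit. Only the first is part of the primary endpoint. On vital signs the same section says: "Vital signs data will include semi supine systolic and diastolic blood pressure, pulse rate, respiratory rate and temperature measurements".

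SAP 4.7 states: "There were no changes or deviations to the originally planned statistical analysis".

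The timing comes from the Part C schedule in protocol 1.3. Footnote 7 is attached to vital signs on every day from Day 1 to Day 7 and reads "7. Predose only". Footnote 8, for the safety ECG, reads "On treatment days ECGs will be collected at predose and 6-hours post-dose".

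**The concern.** A parameter named in the protocol's primary safety endpoint is missing from the SAP section that implements that endpoint, and the SAP says nothing was changed. A programmer who followed the SAP to the letter would tabulate four ECG parameters instead of five.

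Pulse rate is kept under vital signs, so the omission would matter little if vital signs were measured after dosing. In Part C they are not measured after dosing on any dosing day. What is at stake is the summary of heart rate in the hours after dosing in the asthma cohort, the only patients in the study. These data are collected: protocol 8.1.3.2 requires an ECG machine that computes heart rate automatically.

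**Working it through.** The plan gives no figure on this point to reproduce. The check compares the parameter lists and then counts scheduled time points.

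**Step 1. Parameter lists, protocol 9.4.1.2 against SAP 4.2.2.2.**

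| Data type | Protocol | SAP | Match |
|---|---|---|---|
| Laboratory | haematology, chemistry, urinalysis | same | yes |
| Vital signs | systolic and diastolic pressure, pulse, respiration, temperature | same | yes |
| Spirometry | FEV1, FVC | same | yes |
| ECG | heart rate, PR, QRS, QT, QTcF | PR, QRS, QT, QTcF | no: heart rate missing |

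Three of the four lists agree item by item. Only the ECG list loses an entry, which looks more like an oversight than deliberate shorthand.

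**Step 2. Part C heart-rate sources by day (protocol 1.3, Part C schedule and footnotes 7 to 9).**

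| Day | Vital signs | Safety ECG | Same-day post-dose reading |
|---|---|---|---|
| -1 | yes | yes | not a dosing day |
| 1 | pre-dose | pre-dose and 6 h | ECG (telemetry also runs to 6 h) |
| 2 | pre-dose | pre-dose and 6 h | ECG |
| 3 | pre-dose | none | none |
| 4 | pre-dose | pre-dose and 6 h | ECG |
| 5 | pre-dose | none | none |
| 6 | pre-dose | pre-dose and 6 h | ECG |
| 7 | pre-dose | pre-dose and 6 h | ECG |
| 8 | yes | yes | 24 h after the last dose |

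Post-dose vital signs are scheduled on 0 of the 7 dosing days, and post-dose ECGs on 5 of 7.

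**Step 3. Count.** Inputs: 5 days with a 6-hour ECG; 16 participants, 12 active and 4 placebo (protocol 1.1).

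- Active: 5 × 12 = 60
- Placebo: 5 × 4 = 20
- Total: 60 + 20 = 80

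Same-day post-dose heart-rate values covered by the SAP's listed parameters: 0 per participant as written, and up to 5 per participant once ECG heart rate is added.

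**Step 4. What the pre-dose ECGs add.** On the five ECG dosing days the pre-dose ECG coincides with a pre-dose vital-signs assessment, so pulse rate already covers that time. The information lost is the 6-hour reading.

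**The case against.** Several arguments run the other way.

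- **The SAP wording is not strictly exclusive, and other text is unseen.** SAP 1 and 4.2.1 leave the displays and all ranges of potential clinical interest to the Output and Programming Specification, which is not among the documents, and part of SAP 4.2.2.2 is redacted. Heart rate might be restored there. This limits certainty about what will finally be tabulated. It does not cure the SAP: a programming document implements the SAP's parameter list and should not be where a primary-endpoint parameter first appears.
- **A reader might infer that a clinically important heart-rate effect in asthmatics would escape the primary endpoint altogether.** The documents do not support that. Adverse events are also a primary endpoint. Protocol 10.3.1 makes an ECG or vital-sign abnormality an adverse event when the investigator judges it clinically significant, and safety ECGs are read on site. The gap concerns shifts and out-of-range values not reported as adverse events.
- **A reader might infer that the 6-hour ECG is the only post-dose heart-rate measurement in Part C.** Telemetry on Day 1 also runs to 6 hours after dosing. The visible SAP plans no analysis of it, and it covers the first dose only.
- **Heart rate is recoverable.** With Fridericia's formula, QTcF = QT / RR^(1/3) with RR in seconds, so heart rate = 60 × (QTcF / QT)^3. That is true, but no such derivation is planned. It shows that the omission is cheap to repair.
- **Post-dose pulse rate is summarised elsewhere.** Part A has vital signs after dosing, and its planned top dose equals the planned Part C dose. This is reassuring for healthy participants but supplies nothing on asthmatics.
- **A reader might extend the point to Part B or to early time points in Part A.** The Part B vital-signs row is broken in the text available, so no conclusion about its coverage is safe. An early Part A ECG without vital signs at the same minute is of no consequence, because post-dose vital signs follow soon after.

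**Conclusion.** The point holds as an undeclared mismatch between protocol and SAP on a primary safety parameter, with a practical effect in Part C. The SAP's listed parameters cover no same-day post-dose heart rate in asthmatics, although up to 80 such readings (60 active, 20 placebo) are scheduled. The count assumes that all 16 participants complete, and it relies on the ECG days as they appear in the Part C schedule.

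The data are not lost, heart rate is still partly covered through pulse rate, and the study is descriptive, so no test or sample-size statement is affected. Confidence is high on the mismatch between the lists. It is lower on what the final tables will contain, because the programming specification is unseen and some SAP text is redacted. The SAP should be corrected.

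**What to change.** In SAP 4.2.2.2, put heart rate at the head of the ECG parameter list, ahead of PR, QRS, QT and QTcF, so that it enters both the clinically significant values table and the change-from-baseline table. Set its range of potential clinical interest in the Output and Programming Specification, where SAP 4.2.1 places all the others. If the omission is intended, declare and justify it in SAP 4.7 instead.

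The cost is one extra parameter in existing tables. No new data collection or change to the visit schedule is needed.
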